6.2.7 Exploratory evaluations

6.2.7.1 Parts A and B

The following exploratory parameters will be evaluated using ad-hoc descriptive analysis in **Parts A** and **B** based on ITT and PP:

- The effect of Givinostat on each single response parameter according to the clinico-haematological ELN (for PV and ET) [21] (see [paragraph 4.6.1](#)) and EUMNET response criteria (for MF); note that only in case the enrolment in **Part A** is slow (i.e. **< 5 patients enrolled in 3 months**, the eligibility for this part of the study may be expanded to all patients with cMPN).
- Effects of Givinostat on PD markers.
- Effects of Givinostat on spleen size in patients with confirmed splenomegaly at baseline.
- Improvement of constitutional symptoms evaluated according to MPN-SAF QOL questionnaire [24, 32].
- Reduction of the JAK2^{V617F} allele burden, tested by quantitative RT-PCR.
- Reduction of the symptomatic treatment of pruritus in term of dosage and/or days of treatment.

The following exploratory parameters will be evaluated using ad-hoc descriptive analysis in **Part B** based on ITT and PP:

- The preliminary efficacy of Givinostat **after 6 cycles** of treatment according to the “new” ELN criteria (i.e. **revised** ELN response criteria) [33] (see [paragraph 4.8.7](#)).
- The effect of Givinostat on single parameters of the “new” ELN criteria (i.e. **revised** ELN response criteria) [33] (see [paragraph 4.8.7](#)).

Explorative endpoints will be summarized by descriptive methods. Default summary statistics and changes from baseline (where applicable) to each time point for all parameters will be produced.

6.2.8 Other Safety evaluation

All patients who receive at least one dose will be included in the safety evaluation. Safety data including laboratory evaluations, physical exams, ECG monitoring and vital signs assessments will be summarized at each time point. Descriptive statistics

(arithmetic mean, standard deviation, median, minimum and maximum) will be calculated for quantitative safety data as well as for the difference from baseline, if applicable. Frequency counts will be compiled for classification of qualitative safety data. In addition, a shift table describing out of normal range shifts (low/normal/high values) will be provided for clinical laboratory results. A normal-abnormal shift table will also be presented for physical exam and ECG results.

6.2.9 Interim analyses

Italfarmaco S.p.A. will perform a preliminary analysis of data after the completion of the first cycle of treatment from all patients recruited in **Part A**, in order to assess the MTD to be used for **Part B**.

Moreover, a preliminary analysis will be performed on the 12 patients of the first stage of **Part B**: if six or fewer responses will be observed during the first stage then the study will be stopped; if seven or more responses will be observed in the first stage of **Part B**, further 16 patients will be enrolled in the second stage of **Part B**. In this case, a final statistical analysis will be performed considering all patients enrolled in the two study phases.

In addition, Italfarmaco S.p.A. can perform a preliminary analysis of data in case of necessary safety and efficacy updates (e.g. to update regulatory documents and/or the drug safety profile, to revise the development program).

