4.3.3.3 Treatment interruption and treatment discontinuation in *Parts A and B*

In some circumstances, it may be necessary to temporarily interrupt treatment as a result of adverse experiences that may have an unclear relationship to study drug. Study drug may be withheld by the Investigator at any time if there is concern about patient safety and for all aspects of the conduct of the protocol, since the safety of the individual patient is paramount. Treating Investigator may employ any means necessary to ensure patient safety, particularly in medical circumstances not anticipated by this protocol.

Dose adjustments are permitted for patients who do not tolerate the protocol-specified dosing schedule, in order to allow to these patients to continue the treatment with Givinostat (see [paragraph 4.3.3.1](#) and [paragraph 4.3.3.2](#)). The objective of the Givinostat dose adjustment rules described below is to optimize the response for each individual patient, avoiding specific drug-related toxicities.

If the patient inadvertently misses a drug dose, no additional trial medication should be taken that day or in the next days in the effort to replace the material that has been missed.

If vomiting occurs, no additional trial medication should be taken that day in an effort to replace the material that has been vomited.

If the study drug is interrupted for any reason for more than 4 weeks continuously, dosing may be not be restarted.

Patients have the right to withdraw from the study at any time for any reason. The Investigator has the right to withdraw patients from the study due to medical reasons according to his/her discretion.

When patients discontinue study medication, the reason must be categorized in the case report form (CRF) as one of the following:

1. study completed;
2. adverse event(s);
3. disease progression;
4. protocol violation;
5. patient withdrew Informed Consent Form;
6. lost at follow-up (despite every effort made to contact the patient);

7. physician decision due to safety reasons;
8. sponsor decision (see [paragraph 8.7](#));
9. lack of compliance;
10. patient found not eligible;
11. death;
12. pregnancy.

If a pregnancy occurs, the patient will be replaced and another patient in that DL should be recruited.

If the patient discontinues the study because of an adverse event whether or not drug related, he/she must be followed until resolution or stabilization of the event, whichever occurs first.

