6.2.6.2 Part B

The following secondary efficacy parameter will be evaluated in **Part B after 6 cycles of treatment** (i.e. at the end of Cycle 6) based on ITT and PP:

- Preliminary effectiveness of Givinostat (secondary endpoint) after 6 cycles of treatment in **Part B** for PV/ET and MF patients, respectively (see [paragraph 4.6.1](#) for more details):
 - **For PV and ET (if any):** Complete response (CR) and partial response (PR) rate according to the clinico-haematological ELN response criteria [21] (see [paragraph 4.6.1](#));
 - **For MF (if any):** Complete response (CR), major response, moderate response and minor response rate according to the EUMNET response criteria (see [paragraph 4.6.1](#)).

Note that only in case the enrolment in **Part A** is slow (i.e. < 5 patients enrolled in 3 months), the eligibility for this part of the study may be expanded to all patients with cMPN.

Frequency and percentage of patients in each response category (complete response (CR), partial response (PR), no response (NR) for PV and ET; Complete response (CR), major response, moderate response and minor response rate for MF) will be presented at each time point. In order to evaluate the response rate, subjects who discontinued prematurely the study for any reason (AE, consent withdrawal, lost to follow up) will be defined as ‘Non Responder’. Other missing data will not be replaced, if not otherwise specified.

The following secondary safety parameter will be evaluated in **Part B after 6 cycles of treatment** (i.e. at the end of Cycles 6, or including data related to Cycles 4, 5 and 6) based on safety population:

- Number of patients experiencing adverse events.
- Type, incidence, and severity of treatment-related adverse events, graded according to Common Terminology Criteria for Adverse Events (CTCAE v. 4.03, 14th June 2010).

AEs will be coded using MedDRA dictionary (using the most updated version). Adverse events (AEs) will be reported on a per subject basis. If a patient has more than one AE for a treatment that coded to the same preferred term (PT), the patient will be counted only once for that preferred term. Similarly, if a patient has more than one AE for a treatment within a system organ class (SOC) category, the patient will be counted only once in that system organ class category. A patient with multiple CTCAE grades for an AE will be summarized under the maximum CTCAE grade recorded for the event.

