6.3 Sample size and power considerations

A standard 3+3 design adopting a modified Fibonacci escalation schema will be used in **Part A** [25, 26, 27].

Sample size for **Part B** was discussed for the primary end point defined as the Overall Response Rate after 3 cycles. Simon's 2-stage design will be employed in **Part B** [30] with the aim of testing the "null hypothesis" that $RR \leq 0.50$ versus the "alternative" that $RR \geq 0.75$. Response rate will be assessed as defined in [paragraph 6.2.5.2](#). Overall up to 28 patients will need to be recruited, 12 patients being enrolled in Stage-1. PV patients enrolled at the MTD in **Part A** may be counted towards Stage 1. Under the "null hypothesis" (if $RR = 0.50$), the expected total sample size is of 18.2 patients, the probability of early termination at the end of Stage-1 is 0.613 and the probability of rejecting the "null hypothesis" is 0.081 (the target for the type-I error being 0.100). Under the "alternative hypothesis" (if $RR = 0.75$), the probability of rejecting the "null hypothesis" in favour of the "alternative" is 0.902 (the type-II error being 0.098). After testing the treatment on 12 patients in Stage-1, if 6 or fewer patients respond to the treatment the trial will be terminated rejecting the "alternative" that $RR \geq 0.75$. Otherwise, the trial goes on to Stage-2 enrolling further 16 patients to a total of 28 patients. If at the end of Stage-2, a total of 17 or fewer patients respond to the treatment the "alternative hypothesis" that $RR \geq 0.75$ will be rejected; alternatively, if 18 or more patients respond, the "null hypothesis" that $RR \leq 0.50$ will be rejected. Estimations are

obtained from proprietary software (based on SAS ® 9.2) according to the algorithm proposed by R. Simon [30].

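### If a failed Stage 1 also ends participation for ongoing patients, the any-reason Non Responder rule scores them as Cycle 6 failures and lowers the secondary 6-cycle response rate

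*Protocol*

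**What the plan says.** Four parts of the protocol meet here.

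- **The stop.** For the first stage of Part B, Section 6.2.9 states that "if six or fewer responses will be observed during the first stage then the study will be stopped". Section 6.3 words it as "if 6 or fewer patients respond to the treatment the trial will be terminated". The synopsis and Section 6.2 repeat the rule. None of these places says whether patients already on treatment are included.
- **The visit that triggers it.** Section 6.3 bases the design on the "primary end point defined as the Overall Response Rate after 3 cycles", which Section 4.1 places at week 12.
- **The endpoint affected.** Section 6.2.6.2 makes response after 6 cycles (week 24) the secondary efficacy measure of Part B. Its scoring rule is that "subjects who discontinued prematurely the study for any reason (AE, consent withdrawal, lost to follow up) will be" classed as Non Responder. The next sentence adds: "Other missing data will not be replaced, if not otherwise specified".
- **Sponsor-initiated stops.** Section 4.3.3.3 lists the coded reasons for discontinuing study medication. The eighth begins "sponsor decision (see" and points to Section 8.7, on the sponsor's right to terminate the study. Section 6.2.6.2 makes no exception for it.

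**The concern.** The stop is decided on the Cycle 3 result, while the 6-cycle rate needs 12 more weeks of follow-up. At the look, Stage 1 patients who entered within roughly the last 12 weeks of accrual lie between the two visits. If they are taken off study because Stage 1 failed, they have discontinued early, and under the any-reason wording they count as Cycle 6 failures. That includes patients who were responding at Cycle 3.

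The reported 6-cycle rate would then depend on how fast Stage 1 enrolled as well as on the drug. This is a consequence of a rule the protocol states, and it arises in the outcome that the design makes most likely under its own null hypothesis.

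**Working it through.** **Design figures reproduced.** Inputs from Section 6.3: 12 patients in Stage 1, stop at 6 or fewer responses; 28 in total, 18 or more needed to reject; response rates 0.50 and 0.75.

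- Probability of stopping: P(X ≤ 6 | n = 12, p) = 0.6128 at p = 0.50 and 0.0544 at p = 0.75.
- Expected sample size at 0.50: 12 + 16 × (1 − 0.6128) = 18.20.
- Probability of rejecting the null, summing P(X1 = x) × P(X2 ≥ 18 − x | 16, p) over x = 7 to 12: 0.0815 at 0.50 and 0.9017 at 0.75.

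These agree with the protocol's 0.613, 18.2, 0.081 and 0.902. The protocol does not print the 0.054.

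**Bias after a stop.** Let k be the number of Stage 1 patients who have not reached Cycle 6 when the study stops, and p6 the true Cycle 6 response rate, with earlier dropouts already counted as failures. Assume all 12 patients are in the ITT set. The k truncated patients contribute no responses but stay in the denominator:

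- expected reported rate = p6 × (12 − k)/12
- bias = −p6 × k/12, which is never upward.

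**How large k could be.** Part B accrual is not stated. Assume even accrual of a patients per 12 weeks and an immediate stop when the twelfth patient reaches week 12. Entries are then 12/a weeks apart. The patient who entered j places before the last is short of week 24 if j × 12/a < 12, that is, if j < a. Counting j = 0, 1, …, 11 gives k.

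The rate p6 is also not stated; 0.40 is an assumption. For orientation, given a Stage 1 stop at a response rate of 0.50, the expected Cycle 3 rate is 4.896/12 = 0.408.

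| Patients per 12 weeks (assumed) | k | Reported rate if p6 = 0.40 | Bias for p6 = 0.30 to 0.50 (percentage points) |
|---|---|---|---|
| 3 | 3 | 0.40 × 9/12 = 0.30 | −7.5 to −12.5 |
| 4.6 | 5 | 0.40 × 7/12 = 0.233 | −12.5 to −20.8 |
| 6 | 6 | 0.40 × 6/12 = 0.20 | −15 to −25 |
| 12 | 12 | 0 | −30 to −50 |

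The second row is close to 5 patients in 3 months (5 × 12/13 = 4.6). The protocol uses that pace as its slow-enrolment threshold for Part A. It is not a forecast for Part B.

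**Limit from Part A.** Section 6.3 lets PV patients treated at the MTD in Part A count towards Stage 1, and the Amendment 2 rationale reports six patients at that dose level. If all six count and have already passed Cycle 6, k is at most 12 − 6 = 6.

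**The case against.** The strongest reply is that stopping may mean only that Stage 2 does not open. Sections 6.2.9 and 6.3 both set the stop against enrolling 16 further patients, and Section 4.9 ends the study once all patients have had their last scheduled assessment. On that reading Stage 1 patients go on to Cycle 6, k is 0 and there is no bias. This stands as a possible reading, but no section says that treated patients continue after a failed Stage 1.

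Second, the bracketed examples in the Non Responder rule are all patient-level events, so visits lost to a study closure might instead fall under the sentence on other missing data. That too is possible, but the words before the bracket cover any reason, and sponsor decision is a coded reason. If closure did fall under other missing data, the denominator would still be unstated.

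Third, Section 6.2.9 ties the final analysis to the case where Stage 2 opens, and Section 6.2 leaves full detail to an SAP. The SAP could settle the matter. Even so, Section 6.2.6.2 already states its rule for the 6-cycle rate without condition.

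Fourth, the size rests on unstated inputs, and any delay between the twelfth patient's week 12 visit and the decision reduces k. This stands in full.

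**Conclusion.** The point holds conditionally. If Stage 1 fails and the stop is applied to ongoing patients, the rule in Section 6.2.6.2 lowers the 6-cycle rate by p6 × k/12. With p6 = 0.40 that is 10 points at k = 3 and 20 points at k = 6. These figures assume even accrual, an immediate look and an illustrative p6. They show a range and do not predict a result.

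The documents do not support four stronger readings that a reader might draw:

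- That the protocol definitely takes treated patients off at a futility stop. It leaves this open.
- That such patients go wholly unassessed. The end-of-study visit in Section 4.5.4.2.5 includes an ELN response evaluation for patients who leave early; only the Cycle 6 evaluation is missing.
- That the distorted rate would drive the sponsor's development decision. Nothing gives it that role, and after a Stage 1 stop the Cycle 3 result has already rejected the alternative.
- That the trial's inference is damaged. The 6-cycle rate is a descriptive secondary summary; the primary endpoint and the Simon error rates do not change.

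**What to change.** In Section 6.2.6.2, exempt from the Non Responder rule those patients who were discontinued solely because of the Stage 1 futility stop. Report them as not assessed at Cycle 6, state their number, and list their exit ELN evaluations separately. Give the Cycle 6 rate among patients whose scheduled Cycle 6 date came before the stop, still counting those of them who dropped out earlier for other reasons as Non Responders. If entry date is unrelated to response, the −p6 × k/12 term then disappears.

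Reconcile Sections 6.2.9, 6.3 and 4.9 on whether the stop covers enrolment only or also ongoing participation. Which of the two is intended is for the sponsor to state.

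The change takes a few sentences and alters no design figure. Its cost is a smaller Cycle 6 denominator after a futility stop: 12 − k, so 9, 7 or 6 patients for k = 3, 5 or 6, and no Cycle 6 rate at all if k = 12. If stopping turns out to mean enrolment only, the exemption is never used.

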6.3 Sample size and power considerations

A standard 3+3 design adopting a modified Fibonacci escalation schema will be used in **Part A** [25, 26, 27].

Sample size for **Part B** was discussed for the primary end point defined as the Overall Response Rate after 3 cycles. Simon's 2-stage design will be employed in **Part B** [30] with the aim of testing the "null hypothesis" that $RR \leq 0.50$ versus the "alternative" that $RR \geq 0.75$. Response rate will be assessed as defined in [paragraph 6.2.5.2](#). Overall up to 28 patients will need to be recruited, 12 patients being enrolled in Stage-1. PV patients enrolled at the MTD in **Part A** may be counted towards Stage 1. Under the "null hypothesis" (if $RR = 0.50$), the expected total sample size is of 18.2 patients, the probability of early termination at the end of Stage-1 is 0.613 and the probability of rejecting the "null hypothesis" is 0.081 (the target for the type-I error being 0.100). Under the "alternative hypothesis" (if $RR = 0.75$), the probability of rejecting the "null hypothesis" in favour of the "alternative" is 0.902 (the type-II error being 0.098). After testing the treatment on 12 patients in Stage-1, if 6 or fewer patients respond to the treatment the trial will be terminated rejecting the "alternative" that $RR \geq 0.75$. Otherwise, the trial goes on to Stage-2 enrolling further 16 patients to a total of 28 patients. If at the end of Stage-2, a total of 17 or fewer patients respond to the treatment the "alternative hypothesis" that $RR \geq 0.75$ will be rejected; alternatively, if 18 or more patients respond, the "null hypothesis" that $RR \leq 0.50$ will be rejected. Estimations are

obtained from proprietary software (based on SAS ® 9.2) according to the algorithm proposed by R. Simon [30].

7. ETHICS AND GOOD CLINICAL PRACTICE

The investigator will ensure that this study is conducted in full conformity with the principles of the “Declaration of Helsinki” or with the laws and regulations of the country in which the research is conducted, whichever affords the greater protection to the individual.

The study must fully adhere to the principles outlined in “Guideline for Good Clinical Practice” ICH Tripartite Guideline or with local law if it affords greater protection to the subject.

For studies conducted in the EU/EEA countries, the investigator will ensure compliance with the EU Clinical Trial Directive [2001/20/EC] and according to country regulation.

For studies conducted in the USA or under US IND, the investigator will additionally ensure adherence to the basic principles of “GCP” as outlined in the current version of 21 CFR, subchapter D, part 312, “Responsibilities of Sponsors and Investigators”, part 50, “Protection of Human Subjects”, and part 56, “Institutional Review Boards”.

This study will also be carried out in accordance with Italfarmaco S.p.A.’s SOPs.

The investigator agrees, when signing the protocol, to adhere to the instructions and procedures described in it and thereby to adhere to the principles of GCP that it conforms to.

7.1 Institutional Review Board/Ethics Committee

Before implementing this study, the protocol, the proposed informed consent form and other information to patients, must be reviewed by a properly constituted Institutional Review Board/Ethics Committee (IRB/EC). A signed and dated statement that the protocol and informed consent have been approved by the IRB/EC must be given to Italfarmaco S.p.A. before study initiation. The name and occupation of the chairman and the members of the IRB/EC must be supplied to Italfarmaco S.p.A.. Any amendments to the protocol, other than administrative ones, must be approved by this committee.

7.2 Informed consent

Prior to the beginning of the study, the investigator must have the ECs/IRB written approval/favourable opinion of the written Informed Consent and any other written information to be provided to patients or legally authorized representative. The approved patient information letter/Informed Consent must be filed in the study files (TMF and IF).

Written informed consent must be obtained before any study specific procedure takes place.

Clinical Study Protocol
Version 3.0 – 29th July 2015

The investigator must explain to each patient (or legally authorized representative) the nature of the study, its purpose, the procedures involved, the expected duration, the potential risks and benefits involved and any discomfort it may entail. Each patient (or legally authorized representative) must be informed that participation in the study is voluntary, that the patient may withdraw from the study at any time for any reason and that withdrawal of consent will not affect his/her subsequent medical treatment or relationship with the treating physician.

This informed consent should be given by means of a standard written statement, written in non-technical language. The patient (or legally authorized representative) should read and consider the statement before signing and dating it, and should be given a copy of the signed document. If written consent is not possible, oral consent can be obtained if witnessed by a signed statement from one or more persons not involved in the study, mentioning why the patient was unable to sign the form.

8. ADMINISTRATIVE PROCEDURES

8.1 Changes to the protocol

Any change or addition to this protocol requires a written protocol amendment that must be approved by Italfarmaco S.p.A..

Amendments can be classified as substantial when impact one of the following criteria:

- The safety or physical or mental integrity of the patient;
- The scientific value of the study;
- The conduct or management of the study;
- The quality or safety of any IMP used in the study.

Substantial amendments require the authorization to the Competent Authority and the positive opinion of the relevant Ethic Committee (EC) before implementation.

In case of urgent safety measures to protect patient against any immediate hazard these measures can be taken without prior authorization from the Competent Authority or favourable opinion of the EC. In this case the Competent Authority and EC will be informed as soon as possible using the fastest means of communication followed by a written report.

Amendments classified as non-substantial require only notification to the ECs involved.

A progress report must be submitted to the EC at required intervals and not less than annually.

At the completion or termination of the study, the study center must submit a close-out letter to the EC and Italfarmaco S.p.A..

